## Facilities Available

Describe the availability of physical facilities at the place where the study will be carried out. For clinical and laboratory-based studies, indicate the provision of hospital and other types of patient's care facilities and adequate laboratory support. Point out the laboratory facilities and major equipments that will be required for the study. For field studies, describe the field area including its size, population, and means of communications. (TYPE WITHIN THE PROVIDED SPACE).

In accordance with routine practice, the acute phase of treatment of severely malnourished subjects will take place in the general ward or the special care unit of the CRSC. The subjects will then be transferred to the NRU after the acute phase treatment is over. Existing diagnostic laboratory and radiology facilities of the Centre will be utilized.

## Data Analysis

Describe plans for data analysis. Indicate whether data will be analyzed by the investigators themselves or by other professionals. Specify what statistical softwares packages will be used and if the study is blinded, when the code will be opened. For clinical trials, indicate if interim data analysis will be required to monitor further progress of the study. (TYPE WITHIN THE PROVIDED SPACE).

Data will be analyzed using the SPSS Windows software. The Epi Info software will be used to calculate anthropometric indices. Enrollment characteristics will be compared between the three treatment groups. The outcome variables will be compared both within and between groups from enrollment to discharge. For normally distributed quantitative variables, means will be compared by ANOVA. Variables not normally distributed will be log transformed before analysis. Categorical variables will be compared by Chi-square test, multiple or logistic regression will be performed to minimise bias if required.

Results from all randomized children will be included in the analysis of the study. Data from children withdrawn because of failure to respond, TB, or voluntary dropout will be included in the analysis upto the time of withdrawal. A supplementary analysis excluding the children withdrawn may also be made.

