Upon resolution of acute illnesses including diarrhoea, pneumonia, gross electrolyte imbalance, or septicemia, severely malnourished children aged 6 months to 5 years will be randomized to receive any of the three treatment regimens:

1. Home-based nutritional rehabilitation with home follow-up (treatment A, n=75)
2. Home-based nutritional rehabilitation with outpatient follow-up (treatment B, n=75)
3. Hospital-based nutritional rehabilitation (treatment C, n=75).

Children on treatments A and B will stay in the NRU of the CRSC for a period of 7 days, during which their condition will stabilise and their mothers will have learnt the preparation of *khichuri* and *halwa*, which are low-cost, nutritious diets being successfully used in the CRSC. Following discharge after 7 days, these children will continue to be fed *khichuri* and *halwa* prepared by the mothers at home. Children on treatment A will be visited at home for follow-up by health workers at regular intervals during which growth will be monitored, micronutrients supplied, and morbidity recorded. This will continue until the children achieve an oedema-free weight-for-height (WH) >80%. Children on treatment B will be required to attend the outpatient follow-up clinic until they achieve oedema-free WH >80%. Children on treatment C will remain in the NRU and fed *khichuri* and *halwa* according to a standardized dietary schedule until achievement of a WH >80%. Outcome measures that will be used in comparing the three treatments will include growth, time to recovery (achievement of oedema-free WH >80%), rate of weight gain in g/kg per day calculated from lowest weight to discharge weight, speed of loss of oedema, failure to respond, morbidity (number and duration of episodes over equal periods of follow-up for both groups), mortality, and cost of treatment.

KEY PERSONNEL (List names of all investigators including PI and their respective specialties)

Name	Professional Discipline/Specialty	Role in the project
1. [name]	Paediatrician & Nutritionist	P.I.
2. [name]	Internist	Co-investigator
3. [name]	Paediatric Gastroenterologist & Nutritionist	Co-investigator
4. Medical Officer (to be named)	Physician	Co-investigator
5. [name] *	Nutritionist	Collaborating investigator

\* Reader in Community Nutrition  
London School of Hygiene & Tropical Medicine

Principal and co-investigators are from the Clinical Sciences Division, ICDDR,B.

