**Anti-helminthic treatment:** Children >1 year of age will be given mebendazole, 100 mg two times daily for 3 days, if such treatment has not been provided in the last six months. This treatment will be provided after two weeks of nutritional rehabilitation.

**Follow-up:** After the child is discharged from the NRU, a health worker will visit the child every week for one month and then at fortnightly intervals until the child achieves an oedema-free WH >80%. During each visit, the child's general condition will be assessed, weight and height (or length) measured, presence or absence of oedema noted, supplies of micronutrients provided, compliance of feeding and micronutrient supplementation checked by 24 hours recall, and morbidity recorded, if any. To aid recall of morbid conditions, on each visit mothers will be given a pictorial calendar portraying a well child and children with diarrhoea, vomiting, cough, fever, eye infection, or discharging ears [10]. Mothers will be requested to record daily on the calendar whether the condition had been present or absent in the previous 24 hours. Morbidity will then be recorded on a precoded form with the help of the calendar. Diarrhoea will be defined as the passage of three or more watery or liquid stools per day. An episode will be considered new if at least two diarrhoea-free days intervene between the present and previous episodes. The health worker's identification of children with pneumonia of different grades of severity will be based upon WHO guidelines [11]. Lack of weight gain for two consecutive visits will constitute failure to respond. The health worker will refer to the CRSC any child with suspected serious illness, i.e., diarrhoea with some or severe dehydration, pneumonia, ear or throat infection, repeated episodes of fever, loss of appetite, or failure to respond to feeding. Self referral will also be encouraged and entertained at any hour of the day. The child will be evaluated and managed accordingly by any of the investigators (during day time) or the on-duty physician (at night). Readmission to the hospital and the NRU will depend upon existing CRSC guidelines. Any child readmitted to the NRU will not be re-enrolled into the study, but will maintain the pre-readmission status as a study subject. The physician will also record in the precoded form diagnosis, treatment, duration, and outcome of any severe illness including relapse of severe malnutrition or septicemia.

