### **Treatment B**

Children on treatment B will also stay in the NRU for a stabilisation period of 7 days during which their mothers or caretakers will have learnt preparation of khichuri and halwa and taking care of the children at home. Dietary therapy, micronutrient supplementation, training of mothers or caretakers, immunization, and anti-helminthic treatment will be the same as in treatment A. Thereafter, they will be discharged and advised to attend the NFU every week for one month and then at fortnightly intervals until they achieve an oedema-free WH >80%. If a child develops an acute illness or the general condition is not satisfactory at the time of discharge, then the discharge will be postponed till resolution of the illness. The protocol for follow-up will be the same as in treatment A, the difference being that the children will be

brought to the NFU by the parents. If a child fails to attend the NFU within 2 days of a specified follow-up day, a health worker will make a home visit, do the follow-up and reiterate the importance of bringing the child to the NFU for follow-up. The health worker, in course of her follow-up, will try to find out the reason(s) for defaulting. A previous study conducted at the NRU [12] to find out the cause of defaulting showed the principal reason to be the wrong perception of the parents that follow-up was not needed since the child was okay. Other reasons that came up during the previous study, and that will also be inquired during the follow-up visit by the health worker in this study, include: inability of the mother to come to the hospital alone, illness of the mother or child, distance, visit to village homestead, inability to leave other children at home alone, inability to afford the travel expenses, and death of the child.

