### **Treatment C**

Children on treatment C will remain admitted in the NRU until they have achieved an oedema-free WH >80%, and have a good general condition. This will typically involve a stay in the NRU for 15-25 days. The standardized feeding schedule will be followed and micronutrient supplements provided until discharge (refer to treatment A). Training of mothers or caretakers, immunization, and anti-helminthic therapy will be the same as in treatment A, except that in this treatment schedule the mothers or caretakers will receive more educational lessons due to their longer stay in the NRU. Morbid conditions occurring during rehabilitation, including diarrhoea, pneumonia, or septicemia will be recorded in precoded forms. After being discharged from the NRU, the children in this group will be advised to attend the NFU at intervals of two weeks for one month, and then at monthly intervals until they achieve a WH >90%. The entire family will be encouraged to come for the follow-up visit during which preparation of khichuri and halwa will be demonstrated to the mothers and then served to all members. Health education of the mothers or caretakers will be reinforced. Iron supplementation will be continued for 2 months in usual doses. Intercurrent illnesses such as diarrhoea or pneumonia will be treated.

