### **Outcome Measures**

- Time to recovery (achievement of WH 80%, oedema-free), in days
- Rate of weight gain, in g/kg per day calculated from lowest weight to discharge weight
- Speed of loss of oedema, in days
- Failure to respond
- Morbidity, in number and duration of episodes over equal periods of follow-up for both groups
- Mortality
- Cost of treatment

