## Clinical Economics

A complete, cost-benefit analysis from institutional as well as societal perspectives will be performed for all groups, starting from 7 days after randomization (point at which differential costs start). Cost of treatment to the CRSC will include capital and administrative costs, and expenses incurred for food, medicines, and laboratory tests. The cost of treatment to the parents will include expenses incurred for food, wage loss, transport and help needed at home during the mother's absence. This will be done in collaboration with the Health Economics Programme of ICDDR,B.

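### Weight gain and the general comparison window end at discharge, which is about day 7 in A and B but recovery in C, so one end point is needed for all arms

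*Protocol*

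**What the plan says.** Data Analysis sets one general window: "The outcome variables will be compared both within and between groups from enrollment to discharge". Outcome Measures defines the growth rate as "Rate of weight gain, in g/kg per day calculated from lowest weight to discharge weight"; the Project Summary and the abstract for the Ethical Review Committee use the same definition.

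What discharge means depends on the arm:

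- **A and B.** The Project Summary says "Following discharge after 7 days, these children will continue to be fed" the study diets at home. Follow-up comes after that event. For A: "After the child is discharged from the NRU, a health worker will visit the child every week for one month". For B: "Thereafter, they will be discharged and advised to attend the NFU every week for one month". Discharge is delayed only for illness or an unsatisfactory general condition.
- **C.** "Children on treatment C will remain admitted in the NRU until they have achieved an oedema-free WH >80" per cent and are in good general condition. "This will typically involve a stay in the NRU for 15-25 days".

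No later, programme-level discharge is defined for A or B. The Clinical Economics section starts its cost comparison "starting from 7 days after randomization (point at which differential costs start").

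**The concern.** One word fixes two different end points. Followed as written, A and B are measured over the NRU week, when all three arms follow the same standardized diet schedule, and C is measured over its whole rehabilitation. For A and B the window closes just as the arms start to differ.

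This matters most for weight gain, the outcome that gave the largest of the three calculated sample sizes and so set the trial at 75 per arm. A comparison of about 7 NRU days with about 22 NRU days does not address the first hypothesis, that these children can be managed at home.

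The trial cannot be blinded, and both the day-7 weight and the recovery weight will exist for A and B. An analyst could defend either from the text, so the choice should be fixed in advance.

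A second, smaller issue is the start of the interval. The lowest weight can never exceed the final weight, so the rate cannot be negative. A child who loses weight at home and then partly regains it has the baseline reset to the new low.

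**Working it through.** **1. The plan's own figure.** Inputs from Sample Size: hospital weight gain 8.4, SD 7.3 g/kg per day; home-based gain 4; power 90%; type I error 0.05 (two-sided reproduces the figure; one-sided gives 48). With the protocol's formula and a factor of 10.5:

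n = 2 × 7.3² / (8.4 − 4)² × 10.5 = 57.8, so 58 per group, as stated. With 20% dropout, 58 / 0.8 = 72.5, so 73, close to the stated 75. Evaluable children per arm: 75 × 0.8 = 60.

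**2. How much of each course the literal window covers.** Inputs: 35 days assumed for home-based care to WH above 80% and a mean of 22.5 days in hospital (Sample Size); 7 NRU days in A and B.

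- A and B: 7 of 35 days, or 20%. Left out: 35 − 7 = 28 days, or 80%. The 35 days are stated for B; applying them to A is an assumption.
- C: all of its 22.5 days, of which 22.5 − 7 = 15.5 come after the shared week.

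**3. Texts that conflict with that window.**

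- Follow-up under Treatments A and B: children are weighed weekly, then fortnightly, until oedema-free WH above 80%.
- Outcome Measures: time to recovery runs to WH 80%.
- Treatment A: failure to respond is judged over two consecutive follow-up visits.
- Clinical Economics: costs are counted from day 7.
- Sample Size: 35 days are assumed for home-based care.

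**4. If the end point is moved to recovery, does the planned difference survive?** That depends on what the assumed 4 g/kg per day describes.

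- *Whole-course mean.* The difference stays 8.4 − 4 = 4.4, and 58 per group stands. Power with 60 per arm is about 91% (t-test 0.906). If B gains 8.4 in the NRU week, the implied home-phase rate is (4 × 35 − 7 × 8.4) / 28 = 2.9.
- *Home-phase rate only.* If B gains 8.4 in the NRU week, its whole-course mean is (7 × 8.4 + 28 × 4) / 35 = 4.88, and the difference is 8.4 − 4.88 = 3.52. Power with 60 per arm is about 75% (t-test 0.745). The required number is 2 × 7.3² / 3.52² × 10.5 = 90.3, so 91 per group before dropout.

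Both cases keep the SD at 7.3 and use a simple time-weighted mean.

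**The case against.** The strongest reply is that the intent is clear and the data will exist. Weight, height, oedema and morbidity are recorded at every follow-up visit until recovery. Time to recovery, failure to respond, morbidity (over equal periods) and cost each have a definition that reaches into the home phase. Data Analysis itself keeps children withdrawn for failure to respond up to the time they leave, which makes little sense with a day-7 cut-off. All of this stands, and it limits the point to weight gain and the one general sentence. It does not remove the point, because no text gives A and B another discharge.

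A reader might infer three stronger things, which the documents do not support:

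- *The home phase is not measured.* It is; only the stated analysis window misses it.
- *The expected difference between arms is zero.* That would hold for equal 7-day windows with equal gains. The literal windows are unequal, so the contrast is uninterpretable rather than necessarily null.
- *The trial is underpowered.* That follows only if 4 g/kg per day is the home-phase rate. Sample Size attributes it to the home-based method and pairs it with 35 days, so a whole-course mean is an equally good reading.

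There is also a case for the lowest weight as a start: losing oedema lowers weight, and the investigators' reply on oedema gives a median of 7 days to resolution in the NRU. Many lowest weights may therefore fall around or after day 7. Weight loss at home is not wholly hidden either, since it can lengthen time to recovery or count as failure to respond. These are reasons to keep a day-7 start as a sensitivity analysis rather than impose it as the main one.

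**Conclusion.** The point holds as a contradiction in the protocol's wording. Weight gain and the general window end at different events in different arms. Taken literally, they omit about 28 of 35 assumed days (80%) of home-based care while counting all of C's rehabilitation. This affects the outcome that set the sample size; the other main outcomes are largely protected by their own definitions. The 80% rests on the protocol's 35-day assumption and on discharge at day 7 without postponement.

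The effect on power is a range, not a finding of low power: from 58 per group and about 91% to 91 per group and about 75%, depending on which rate the 4 g/kg per day describes.

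**What to change.** 1. In the Project Summary, Outcome Measures, Data Analysis and the abstract for the Ethical Review Committee, replace discharge as the end of measurement with one end point for all arms: the first recorded oedema-free WH above 80%, or the last study weight if that is not reached. This changes only what is analysed, not when any child leaves the NRU.
2. Add a sensitivity analysis of the rate from the day-7 weight, where the protocol says costs diverge, to the same end point. Show children still oedematous on day 7 separately. Do not start them at their first oedema-free weight: that is a post-randomization outcome whose timing may differ by arm (medians of 19 days at home and 11 as inpatients in the earlier Dhaka study cited in the reply on oedema).
3. State in Sample Size whether 4 g/kg per day is a whole-course or a home-phase rate. If it is home-phase, restate the power.

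The cost is wording and slightly more analysis. The follow-up weights are already planned.

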### **Hypothesis to be tested:**

1. After an initial period of hospitalization, severely malnourished children recovering from diarrhoea can be managed at home using indigenous, low-cost, and culturally acceptable diets.
2. The cost-benefit of a home-based programme for nutritional rehabilitation of severely malnourished children recovering from diarrhoea will be more than the conventional hospital-based programme.

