### Enrollment Criteria

Age:	6 months to 5 years
Gender:	Either
Nutritional status:	Severely malnourished (WH < 70% of the NCHS median or with oedema)
General condition:	Resolution of acute illness including diarrhoea, pneumonia, gross electrolyte imbalance, and septicemia. Criteria of resolution of acute illnesses are outlined under management of acute illness .
Place of residence:	Within 10 km from the CRSC (for convenience of follow-up)

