### **Treatment A**

In this treatment schedule, children will stay in the NRU for 7 days during which period their clinical condition will stabilise, and their mothers or caretakers will have learnt preparation of khichuri and halwa and taking care of the children at home. Thereafter, they will be discharged and health workers will visit them at their homes at regular intervals until they achieve a WH >80%, are free of oedema, and have a good general condition. If a child develops an acute illness or the general condition is not satisfactory at the time of discharge, then the discharge will be postponed till resolution of the illness. During stay in the NRU, calories and protein are gradually increased over a period of time in a programmed way in order to achieve rapid growth involving a weight gain of more than 10 g/kg per day. A major element of the method of nutritional rehabilitation practised in the NRU of the CRSC is that the diet given to the children contains proteins derived mainly from vegetable sources. Food containing animal protein such as milk (which is given only initially), eggs, meat or fish are expensive, and the mothers of these children can hardly afford these foods when continuing nutritional rehabilitation at home.

The diet schedule to be followed for the children is as shown on the following page. This is the standardized diet schedule that is currently being routinely practiced in the NRU of the CRSC.

Diet	Item & amount	Energy intake Kcal/kg.day	Protein intake g/kg.day
1	Milk suji 10 ml/kg.feed (110ml/kg.day) 2 hrly (11 feeds per day)*	74	1.5
	Halwa 10 g/kg.feed 2 feeds per day	48	1.0
	Total:	122	2.5
2	Milk suji 10 ml/kg.feed (110ml/kg.day) 2 hrly (11 feeds per day)*	74	1.5
	Halwa 10 g/kg.feed 2 feeds per day	48	1.0
	Khichuri 10 g/kg.feed 2 feeds per day	29	0.6
	Total:	151	3.1
3	Milk suji 100 10 ml/kg.feed (110ml/kg.day) 2 hrly (11 feeds per day)*	110	2.8
	Halwa 10 g/kg.feed 2 feeds per day	48	1.0
	Khichuri 10 g/kg.feed 2 feeds per day	29	0.6
	Total:	187	4.4
4	Milk suji 100 10 ml/kg.feed (110ml/kg.day) 2 hrly (11 feeds per day) *	110	2.8
	Halwa 10 g/kg.feed 3 feeds per day	72	1.5
	Khichuri 10 g/kg.feed 3 feeds per day	43	0.9
	Total:	225	5.2
5	Milk suji 100 10 ml/kg.feed (40ml/kg.day) 6 hrly (4 feeds per day)	40	1.0
	Halwa 20 g/kg.feed 3 feeds per day	144	3.0
	Khichuri 20 g/kg.feed 3 feeds per day	87	1.8
	Total:	271	5.8

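### Within-arm change from enrolment to discharge cannot show whether home care works, and the analysis end point needs one definition for all arms

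*Protocol*

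**What the plan says.** The Data Analysis section plans two comparisons in one sentence: "The outcome variables will be compared both within and between groups from enrollment to discharge". It then names the method for quantitative outcomes: "For normally distributed quantitative variables, means will be compared by ANOVA". Nothing there or elsewhere in the protocol calls the within-group part descriptive or says what it is for.

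The first hypothesis is worded as a statement about home care alone: after an initial hospital stay, "severely malnourished children recovering from diarrhoea can be managed at home using indigenous, low-cost, and culturally acceptable diets".

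Discharge does not mean the same thing in the three arms:

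- Treatment A: "In this treatment schedule, children will stay in the NRU for 7 days", then discharge home.
- Treatment B: "Children on treatment B will also stay in the NRU for a stabilisation period of 7 days", then discharge with clinic follow-up.
- Treatment C: children "will remain admitted in the NRU until they have achieved an oedema-free WH >80"% and are in good general condition. That is also the recovery outcome.

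The entry criterion is "Severely malnourished (WH < 70% of the NCHS median or with oedema"). Under Outcome Measures, the rate of weight gain runs from the child's lowest weight to the weight at discharge.

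**The concern.** A before/after comparison inside a single arm has no control. It is useful only if its result could differ according to whether the treatment works. Here it could not, under either meaning of discharge. At day 7 the gain belongs to the supervised NRU week that all arms share. At the WH target, the end point is defined by the gain being tested.

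Because the first hypothesis has no comparator in its wording, a small within-arm p-value in A or B could easily be reported as support for it.

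The end point causes a related problem between arms. Children who recover all stop just above the same WH, so their change in WH is nearly the same however long it took. If A and B are instead closed at day 7 while C runs to the target, the arms are measured over different periods, and no home care enters the A and B figures.

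**Working it through.** **Inputs.** From Sample Size: NRU gain 8.4 ± 7.3 g/kg/day, NRU time to WH >80% 22.5 ± 6.2 days, assumed outpatient-arm gain 4 g/kg/day, type I error 0.05, power 90%, dropout 20%, 75 per arm. From Enrollment Criteria and Treatment C: entry WH <70% or oedema, exit oedema-free WH >80%. From the reply to the ethics committee: one-third of severely malnourished admissions have oedema.

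**1. The plan's own figure.** Two-sided factor (1.960 + 1.282)² = 10.51. n = 2 × 7.3² / (8.4 − 4)² × 10.51 = 57.9, so 58 as stated. Dropout: 58 / 0.8 = 72.5, so 73 against the stated 75. With 20% lost, 75 × 0.8 = 60 remain.

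**2. Discharge as the end of the NRU week (A and B).** Home care contributes exactly zero. The protocol names no within-group test, so a paired t-test of change against zero is assumed; a repeated-measures ANOVA with two time points gives F = t² and the same p-value. The expected t is (mean / SD) × √n. Over 7 days the gain is 8.4 × 7 = 58.8 g/kg with SD 7.3 × 7 = 51.1, so the ratio is unchanged. Probabilities of p < 0.05 come from the noncentral t. First-week gains below 8.4 are assumptions.

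| First-week gain, SD 7.3 (g/kg/day) | t, n = 60 | P(p<0.05) | t, n = 75 | P(p<0.05) |
|---|---|---|---|---|
| 8.4 | 8.91 | >99.9% | 9.97 | >99.9% |
| 5 | 5.31 | 99.9% | 5.93 | >99.9% |
| 4 | 4.24 | 98.7% | 4.75 | 99.7% |
| 3 | 3.18 | 88% | 3.56 | 94% |
| 2 | 2.12 | 55% | 2.37 | 65% |

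Doubling the SD at 8.4 still gives 99.2% (n = 60) and 99.8% (n = 75).

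**3. Discharge as oedema-free WH >80%.** At constant height, a child going from below 70% to above 80% gains at least 80/70 − 1 = 14.3% in weight. Every wasted completer therefore has a positive change. Information about home care lies in how many children reach the target and how soon, and a test of change against zero uses neither.

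**4. Gain from lowest weight.** The lowest weight cannot exceed the discharge weight, so this gain is never negative. A simulation of 75 children, each with eight noisy weighings and no true gain, was significant in every run.

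**5. Children with oedema.** They need not enter below 70% and may lose weight as oedema clears. With one-third oedematous and an assumed loss subtracted from their 58.8 g/kg, the day-7 test on raw weight is significant in:

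- 50 g/kg lost: 100% (n = 60) and 100% (n = 75)
- 80 g/kg: 97% and 99%
- 100 g/kg: 79% and 88%
- 150 g/kg: 13% and 15%

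**6. Between-arm comparison.** With no difference between arms, three-arm ANOVA on the same change at 60 per arm rejected in 5.2% of simulations. For a rate of 8.4 against 4 g/kg/day, a two-arm comparison has 91% power at 60 per arm and 95.8% at 75.

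**The case against.** The protocol never makes a within-arm p-value the test of the first hypothesis. Its second specific aim is a randomised comparison of home with hospital care, the sample size rests on pair-wise differences between groups, and the quoted sentence itself plans the between-group comparison. All of this stands. A reader might infer that the trial's main inference is lost; the documents do not support that.

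A reader might also infer that the within-arm test cannot fail. That goes too far. Children enrolled with oedema can lose weight. The analysis includes all randomised children, with withdrawn children counted up to withdrawal, so gain by definition applies only to wasted completers. The 8.4 g/kg/day comes from rehabilitation averaging 22.5 days to the target, whereas in the first week the diet is still being stepped up, so a lower first-week gain is plausible.

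Nor are the 98.7% and 99.7% at 4 g/kg/day false-positive rates to set beside 5%. They are the power to detect a real gain; the point is only that the gain was made in the NRU.

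Finally, it may be said that the expected home shortfall would still be seen, because rate of gain and time to recovery both contain time and both are listed outcomes. That is right if the end point is the WH target in every arm. It is not right for the rate if discharge weight in A and B is the day-7 weight.

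What remains is that the protocol fixes an uninformative comparison, does not label it descriptive, and ties it to an end point that differs between arms.

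**Conclusion.** The point holds for weight, WH and weight gain. A within-arm change from enrolment to discharge carries no evidence that home rehabilitation works. On the day-7 reading, significance is close to certain at the protocol's own NRU gain and still more likely than not at an assumed 2 g/kg/day, before any home care; large assumed weight losses in oedematous children could bring it well below that on raw weight. On the target reading, a gain of at least 14.3% is built in for wasted completers. Gain from lowest weight cannot be negative on either reading.

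Time to recovery, mortality, failure to respond and cost have no enrolment value to compare with and are not affected. WH change among recovered children cannot reveal a slower arm; rate of gain and time to recovery can, given one end point for all arms.

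This is a correction worth making to one sentence and one definition. The randomised comparison remains sound. The percentages rest on a paired t-test or its ANOVA equivalent, on the SD of 7.3 applying to the first week, and on the assumed first-week gains and oedema losses shown.

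**What to change.** In Data Analysis:

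1. Replace the quoted sentence with a statement that outcomes are compared between the randomised groups only.
2. Add that within-arm changes are descriptive and are not evidence for the first hypothesis.
3. Define the analysis end point identically for A, B and C: from randomisation to oedema-free WH >80%, or to last follow-up if that is not reached, and not NRU discharge. Give discharge weight under Outcome Measures the same meaning. This matches the sample-size basis, which pairs the gain with the time to WH >80%.

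The cost is wording only. Treatment, visit schedule and sample size do not change.

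A between-arm comparison of WH or weight at a common time from randomisation may be added as supportive. Around day 35 uses existing contacts: the fourth weekly visit in A and B (7 + 28 = 35), and the first clinic visit of an average C child (22.5 + 14 = 36.5). It should not be more than supportive. A is visited at home and B defaulters are traced, but C children are only advised to attend after discharge, so their values may be missing more often. The outpatient arm is also expected to reach the target at about that time.
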